12.2 Laboratory safety variables

All laboratory data will be listed by dose level. In addition, descriptive statistics of routinely measured laboratory safety variables at each visit will be computed. Both the absolute values and changes from baseline will be summarized by dose level. Frequencies of out-of-range values (low, normal or high) and clinically significant values defined by the investigator will be summarized by dose level and visit as shift tables.

12.3 Other safety variables

ECG results (Heart rate, PR, QRS, RR, QT, QTcF and QTcB times) will be listed by dose level and summarized with descriptive statistics by dose level using absolute values and changes from baseline to post-baseline pre-dose values. Moreover, the changes within each visit from pre to post-dose will be summarized. The ECG interpretation (Normal, Abnormal but not clinically significant or Abnormal and clinically significant) and abnormal QTcF and QTcB results (values >500 ms or changes of >30 ms and of > 60 ms) will be listed by dose level and summarized by visit, time point and dose level as shift tables. The QTcF and QTcB times will be calculated based on the following formulas:

$$QTcF = QT / RR^{1/3}$$

$$QTcB = QT / RR^{1/2},$$

where $RR = 60 / HR$.

Vital signs results (ulna length, height based on ulna length, weight, saturation of peripheral oxygen, blood pressure, heart rate, respiratory rate, body temperature, ability to stand, ambulatory status) will be listed by dose level and summarized descriptively by visit, time point and dose level. Absolute values, changes from baseline to post-baseline pre-dose values and within visit changes from pre- to post-dose values will be presented in the summaries.

Liver abdominal ultrasound results (liver span, echogenicity, presence of cysts and tumours, bile duct dilatation, gallbladder filled, presence of stones and portal vein dilatation) will be listed by dose level and summarized descriptively by dose level and visit. For the last visit, information on changes in the ultrasound from baseline will be listed.

13 Disease relevant clinical assessments

All disease relevant clinical assessment variables will be summarized as data listings by dose level. In addition, descriptive statistics/ frequency tables will be included when appropriate. Both absolute values and changes from baseline (if feasible) will be presented. The descriptive statistics/ frequency tables will be broken down by visit. Relevant background status (age of the patient, ambulatory status and type of disease) and AUC_{0-24h} information from PK analysis of plasma concentrations vs time profiles of omigapil will be included in the listings.

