- Histological diagnosis showing (i) absent or significantly decreased expression of collagen VI in muscle (overall reduction or basal lamina specific) or (ii) absent or significantly abnormal matrix in skin fibroblast culture

For patients with Laminin alpha 2 related dystrophy (LAMA2-RD) – required clinical picture

- Muscle weakness: Inability to walk; if patient is still ambulatory, inability to run and > 5 s for 10 m walk.

Genetics and Pathology:

- Either: 2 identified pathologic or probable pathologic mutations in LAMA2 gene
OR
- 1 identified pathologic or probable pathologic mutation in LAMA 2 gene with evidence of decrease in laminin alpha 2 staining on muscle or skin biopsy

OR

- Evidence of decrease in laminin alpha 2 staining on muscle or skin biopsy with matching clinical phenotype and no suspicion of alpha dystroglycanopathy (aDG-RD) (clinically or by staining on muscle biopsy)

Exclusion Criteria

- Use of any investigational drug other than the study medication within 12 weeks of study start.
- Recurrent hospitalization for chest infections in previous 2 years (≥ 2 per year)
- Patients with respiratory parameters (eg: low pulmonary function test value i.e. $<30\%$ predicted or need for daytime non-invasive ventilation) currently affected by short term medications, or acute illness/ conditions (conduct baseline assessments when the patient has recovered and is no longer taking acute medication)
- Any need for surgery (i.e. scoliosis, gastrostomy, other) in the preceding 24 weeks or foreseen during the course of the study.
- Patient has an intercurrent significant medical condition or situation which in the opinion of the Investigator or the study Medical Monitor may put the patient at significant risk, confound the study results or interfere significantly with the patient's participation in the study.
- Failure to thrive, defined as:
 - Falling 20 percentiles (20/100) in body weight in the 12 weeks preceding Screening/Baseline (based on family report of weight loss and review of relevant medical records)
 - In patients below the 3rd percentile, any further drop in body weight percentile in the 12 weeks preceding Screening/Baseline (based on family report of weight loss and review of relevant medical records)
- Weight less than 17 kg at Baseline
- Morbidly obese or grossly overweight (≥ 86 percentile body mass index (BMI) in children)
- History of epilepsy or on antiepileptic medication at Screening/Baseline
- Diabetes

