6.3 Safety dataset

The Safety dataset will include all enrolled patients who received at least one dose of study medication. Safety dataset will be used for all the safety analyses.

7 Disposition of patients

The number of patients enrolled into the study at screening, the number of patients who failed the screening and the reasons for screening failures will be summarized. The number of patients entering and completing the study will be summarized by dose level and overall. Also, the number of patients who discontinued prematurely, the reasons for premature discontinuations and replacement information will be summarized by dose level and overall. The disposition data will also be presented in a listing format.

8 Demographic and other baseline characteristics

All demographic and other baseline characteristics (age, height, weight, body mass index [BMI], gender, ethnicity, race, child-bearing potential, ambulatory status, disease type (LAMA2-RD or COL6-RD), time since CMD diagnosis and use of respiratory aid [Bi-Pap]) will be listed by dose level and summarized with descriptive statistics by dose level. The physical examination findings, medical history and pregnancy test results will be listed by dose level.

Age will be calculated using month of birth and month of baseline (screening) visit as difference in months between baseline and time of birth divided by 12. Height will be estimated from ulna length by using the following formulas (Gauld, 2003, 2004):

$$\text{Height (male, age <20)} = ((4.605 * \text{ulna length [cm]}) + (1.308 * \text{age [years]}) + 28.003$$

Height (female, age < 20) = ((4.459* ulna length [cm]) + (1.315 * age [years])) + 31.485.

Height and weight will also be presented as percentages of normal growth at the age of the patient (Clinical Growth Charts, U.S. National Center for Health Statistics).

9 Concomitant medication/treatment

Concomitant medication and treatments are coded to WHO drug dictionary version September 2017, and will be listed by dose level, including the Preferred term and ATC classification levels 1 and 4.

10 Extent of exposure and compliance

The extent of exposure will be summarized based on the duration of study treatment (days). The duration of study treatment will be listed and summarized with descriptive statistics by dose level.

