14.2.5 Vital signs

Table 14.2.5.1 Descriptive statistics of ulna length, height based on ulna length and weight

Table 14.2.5.2 Descriptive statistics of saturation of peripheral oxygen

Table 14.2.5.3 Descriptive statistics of blood pressure, heart rate, respiratory rate and body temperature

Table 14.2.5.4 Frequency distributions of being able to stand and ambulatory status

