16.2.4 Safety data listings

Listing 16.2.4.1 Adverse events

Listing 18.2.4.2 Vital signs

Listing 18.2.4.3 ECG

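### On-treatment weight in growing children is summarised without reference to age, so the dose-level mean mixes normal growth with any effect of treatment

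*SAP*

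**What the plan says.** SAP 12.3 places weight among the vital signs: "Vital signs results (ulna length, height based on ulna length, weight, saturation of peripheral oxygen, blood pressure, heart rate". These "will be listed by dose level and summarized descriptively by visit, time point and dose level". On the form of the summary it says: "Absolute values, changes from baseline to post-baseline pre-dose values and within visit changes from pre- to post-dose values will be presented in the summaries". The table plan has one entry for weight, "Table 14.2.5.1 Descriptive statistics of ulna length, height based on ulna length and weight", and the listing plan has "Listing 18.2.4.2 Vital signs". Neither section 12.3 nor the table plan gives a post-baseline percentile, z-score or categorical summary of weight.

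An age reference for weight appears in SAP section 8, on demographic and baseline characteristics: "Height and weight will also be presented as percentages of normal growth at the age of the patient". The source given there is the US clinical growth charts.

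The protocol synopsis uses growth percentiles in the failure-to-thrive exclusion criterion. One limb is "Falling 20 percentiles (20/100) in body weight in the 12 weeks preceding Screening/Baseline". The other applies to patients already below the 3rd percentile and counts any further percentile drop over the same 12 weeks. Omigapil is also given for 12 weeks (Visit 2 to Visit 5), after 4 weeks on vehicle.

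**The concern.** For most vital signs, no change is the natural null value. For weight in children it is not: a child who grows normally gains. A mean change in kilograms therefore has a positive expected value that depends on the age mix of the dose group, and nothing in the summary says what that value is. There is no placebo group to supply it, and the run-in lasts only 4 weeks.

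The SAP already recognises the problem elsewhere. Section 13.1 expresses PEF, FVC, FEV1, MEP and MIP as percent predicted, using age at the time of measurement, and references peak cough flow to age as well. Those are tertiary feasibility measures. Weight, which belongs to the secondary safety objective, has no such adjustment after baseline.

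At stake is how the weight table is read. A small positive mean looks reassuring, but it is compatible with one child in the group having lost considerable ground against the growth chart.

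**Working it through.** The documents give no figure to reproduce on this point. The growth inputs below are assumptions, so only direction and range should be relied on. Kilograms is inferred as the unit in SAP 12.3 from its use elsewhere in the documents.

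**Inputs from the documents.** Age 5 to under 17; planned cohorts of 4, 4 and 8-12; 12 weeks of omigapil; Visit 5 falls 16 weeks after Visit 1 (4 weeks of run-in plus 12 of treatment). SAP section 4 reports that four dose levels were used. Spread over four levels, 16-20 patients average 4 to 5 per level (16/4 = 4, 20/4 = 5). The actual sizes are not stated there, so both small and large groups matter.

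**Worked case, 12 weeks.** Assumed: median weight 25 kg at the start, normal gain 0.6 kg (so the median becomes 25.6 kg), log-normal weight-for-age with coefficient of variation (CV) 15%, range 12-18%.

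- Weight at the 30th percentile after 12 weeks: 25.6 × exp(−0.524 × 0.15) = 23.66 kg.
- Change for a child who started at the 50th percentile: 23.66 − 25 = −1.34 kg (−0.96 to −1.71 kg for CV 12-18%).
- Mean change when the other n − 1 children each gain 0.6 kg: [−1.34 + (n − 1) × 0.6]/n.

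| n | Mean change, CV 15% | CV 18% to CV 12% |
|---|---|---|
| 4 | +0.12 kg | +0.02 to +0.21 kg |
| 8 | +0.36 kg | +0.31 to +0.41 kg |
| 12 | +0.44 kg | +0.41 to +0.47 kg |

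**Wider range.** Assumed: median weight and annual gain of 18/2.0, 25/2.5, 35/3.5 and 50/5.0 kg; CV 12, 16 and 20%; normal distribution; one child falling 20 percentiles from the 25th, 50th or 75th. That gives 4 × 3 × 3 = 36 scenarios. With g the normal gain and Δz the fall in SD units, the mean change is g − Δz × SD/n.

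| n | Mean ≥ 0 at 12 weeks | Range | Mean ≥ 0 at 16 weeks (from Visit 1) |
|---|---|---|---|
| 4 | 16 of 36 | −1.27 to +0.37 kg | 28 of 36 |
| 8 | 33 of 36 | −0.06 to +0.76 kg | 36 of 36 |
| 12 | 36 of 36 | +0.17 to +0.89 kg | 36 of 36 |

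The falling child's own change is negative in every scenario, from about −0.5 to −8.6 kg over the two durations.

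**Child below the 3rd percentile.** Assumed: median 23 kg, CV 13%, normal distribution, median gain 2.5 × 12/52 = 0.58 kg over 12 weeks. A child at the 2.5th percentile weighs 23 × (1 − 1.96 × 0.13) = 17.1 kg, just above the protocol's 17 kg floor.

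- Flat weight: z = (17.14/23.58 − 1)/0.13 = −2.10, about the 1.8th percentile.
- Gain of 0.21 kg: z = (17.35/23.58 − 1)/0.13 = −2.03, about the 2.1th percentile.

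In both cases the percentile falls with no weight loss, so neither a listing in kilograms nor a tabulated minimum change would draw attention to it.

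**The case against.** The strongest reply is that nothing is concealed. Weight is listed by patient as well as summarised, the study has about 20 patients, and a child who falls 20 percentiles shows a loss in kilograms in that listing. A minimum, if the descriptive statistics include one, would show it too, and weight loss recorded as an adverse event would be tabulated by preferred term. This stands: for a 20-percentile fall, only the group mean can mask it, and with 4 patients over 12 weeks it stays at or above zero in fewer than half of the scenarios. The reply does not cover the child below the 3rd percentile, whose kilograms need not fall.

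A reader might infer that the plan misses patients who cross a protocol safety threshold. The documents do not support that. Failure to thrive is an eligibility criterion for the 12 weeks before Screening/Baseline, judged from family report and medical records, and no text supplied applies it during treatment. Only the protocol synopsis is available, so on-study weight rules elsewhere cannot be excluded.

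A reader might also compute over the 24 weeks from Visit 1 to Visit 6. With an assumed gain of 1.2 kg, a 1 kg loss then takes a 25 kg child from the 50th to the 28th percentile, and the mean of four is (3 × 1.2 − 1)/4 = +0.65 kg. But that span includes 4 weeks on vehicle and 8 weeks off drug. Over the 12 treatment weeks at the same growth rate, a 1 kg loss leads to about the 33rd percentile, a fall of 17 points, and unchanged weight leads to about the 44th.

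Finally, this is an exploratory phase I study with descriptive summaries, and none of them is invalid as planned. That is fair, and it limits the weight of the point.

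**Conclusion.** The point holds as a weakness in the summary. After baseline, weight is reported only as absolute value and change, in growing children without a control group, although the SAP already applies a growth reference at baseline. Under the stated assumptions, a 20-percentile fall in one child (about 1.3 kg) leaves the mean of four at about +0.1 kg. The sign depends on the assumptions at n = 4 and is almost always positive at n = 8-12. The listing in kilograms covers that case but not a percentile drop with flat or slightly rising weight below the 3rd percentile.

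It would go too far to say that the plan hides a failing child or ignores an on-treatment rule: individual weights are listed, and the percentile criterion shown governs entry only. A z-score would remove normal growth from the summary. Without a control group, it would not separate drug effect from the course of the disease.

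**What to change.** In SAP 12.3 and Table 14.2.5.1, add the weight-for-age z-score (or percentile) by visit and dose level, with change from baseline, using the growth charts cited in section 8 and age at the time of measurement. Add the same variable to the vital signs listing. The z-score is the better choice for patients in the low tail, where percentiles are compressed: in the flat-weight example, z moves from −1.96 to −2.10 while the percentile moves only from 2.5 to 1.8.

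Optionally, tabulate by dose level the number of patients whose fall from Visit 2 to Visit 5 (12 weeks) meets either limb of the protocol's failure-to-thrive definition. Label this as a descriptive benchmark, not as an on-treatment clinical rule.

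The cost is one derived variable, some extra table columns and the SAP wording. Weight is already summarised by visit and the growth reference is already cited, so no new data are needed.

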13.1 Respiratory function testing (hospital spirometry)

Respiratory function tests will be presented as non-normalized values and as percentages of predicted values for Peak Expiratory Flow (PEF), Forced Vital Capacity (FVC), Forced Expiratory Volume during first second of the forced breath (FEV1), Maximum Expiratory Pressure (MEP) and Maximum Inspiratory Pressure (MIP). The equations presented in table 13.1.1 will be used for calculation of the percent predicted values. For the equations presented by race, the Caucasian equation will be used also for the Asian subjects. Due to loss of ambulation/ loss of ability to stand, the height will be estimated from the ulna length for all subjects. Age and height used in the equations will always be the age at the time of the measurement and calculated using month of birth and month of assessment date as time difference in months divided by 12.

Table 13.1.1 Percent predicted equations for respiratory function tests

Value (Reference)	Formula
PEF%p (Hankinson, 1999)	Caucasian Male (age < 20 years): $PEF / ((-0.5962 - (0.12357 * \text{age})) + (0.013135 * (\text{age}^2) + ((0.00024962 * (\text{height}^2)) * 1))) / 60 * 100$ Female (age < 18 years): $PEF / ((-3.6181 + (0.60644 * \text{age})) - (0.016846 * (\text{age}^2) + ((0.00018623 * (\text{height}^2)) * 1))) / 60 * 100$
	Black or African-American Male (age < 20 years): $PEF / ((-0.2684 - (0.28016 * \text{age})) + (0.018202 * (\text{age}^2) + ((0.00027333 * (\text{height}^2)) * 1))) / 60 * 100$ Female (age < 18 years): $PEF / ((-1.2398 + (0.16375 * \text{age})) + ((0.00019746 * (\text{height}^2)) * 1)) / 60 * 100$
FVC%p (Hankinson 1999)	Caucasian Male (age < 20 years): $FVC * 100 / ((-0.2584 - (0.20415 * \text{age})) + (0.010133 * (\text{age}^2) + ((0.00018642 * (\text{height}^2)) * 1)))$ Female (age < 18 years): $FVC * 100 / ((-1.2082 + (0.05916 * \text{age})) + ((0.00014815 * (\text{height}^2)) * 1))$
	Black or African American Male (age < 20 years): $FVC * 100 / ((-0.4971 - (0.15497 * \text{age})) + (0.007701 * (\text{age}^2) + ((0.00016643 * (\text{height}^2)) * 1)))$ Female (age < 18 years): $FVC * 100 / ((-0.6166 - (0.04687 * \text{age})) + (0.003602 * (\text{age}^2) + (0.00013606 * (\text{height}^2)) * 1))$
MEP%p (age < 18) (Domenech-Clar, 2003)	Male: $MEP * 100 / (7.619 + (7.806 * \text{age}) + (0.004 * \text{height} * \text{weight}))$ Female: $MEP * 100 / (17.066 + (7.220 * \text{age}))$
MIP%p (Domenech-Clar, 2003)	Male: $-MIP * 100 / (-27.020 - (4.132 * \text{age}) - (0.003 * \text{height} * \text{weight}))$ Female: $-MIP * 100 / (-33.854 - (1.814 * \text{age}) - (0.004 * \text{height} * \text{weight}))$
FEV1%p (Hankinson 1999)	Caucasian Male (age < 20 years): $FEV1 * 100 / ((-0.7453 - (0.04106 * \text{age})) + (0.004477 * (\text{age}^2) + ((0.00014098 * (\text{height}^2)) * 1)))$

Value (Reference)	Formula
	
Female (age < 18 years): $FEV1 * 100 / ((-0.8710 + (0.06537 * \text{age})) + ((0.00011496 * (\text{height}^2)) * 1))$
 
Black or African American
 
Male (age < 20 years): $FEV1 * 100 / ((-0.7048 - (0.05711 * \text{age})) + (0.004316 * (\text{age}^2)) + ((0.00013194 * (\text{height}^2)) * 1))$
 
Female (age < 18 years): $FEV1 * 100 / ((-0.9630 + (0.05799 * \text{age})) + ((0.00010846 * (\text{height}^2)) * 1))$

The highest respiratory function test value at each visit will be used in the calculations.

Percent predicted values for PCF will be counted by using the 50th percentiles by age presented in table 12.1.2 (Bianchi, 2008) with the following formula: $PCF\%p = PCF * 100 / 50^{\text{th}} \text{ percentile for the age}$. Age used in defining the percentiles will be the age at the time of the measurement and calculated with precision using month of birth and month of assessment date.

Table 13.1.2 Percentile values of peak cough flows (liters/min) by gender and age (Bianchi 2008)

		Females					
Age, yrs	5th	10th	25th	50th	75th	90th	95th
4	110	112	124	147	179	202	209
5	125	132	171	185	219	245	273
6	161	161	191	230	242	284	317
7	179	200	228	247	265	302	330
8	200	219	270	299	321	340	351
9	270	270	290	311	347	369	369
10	270	284	299	330	361	380	399
11	296	299	347	380	399	441	478
12	305	340	361	399	412	450	459
13	311	330	361	395	441	508	545
14	361	372	399	428	478	518	561
15	344	384	424	469	508	550	596
16	358	412	428	469	508	550	626
17	369	416	433	469	513	550	633
18	399	420	441	488	513	556	639
		Males					
Age, yrs	5th	10th	25th	50th	75th	90th	95th
4	130	132	143	162	194	226	230
5	138	153	179	194	226	262	270
6	166	171	204	226	250	279	293
7	200	211	235	270	299	340	351
8	215	247	279	299	321	340	347
9	217	237	293	311	340	372	424
10	250	260	296	321	351	380	428
11	290	299	340	369	399	420	441
12	311	317	334	369	399	450	498
13	321	337	392	450	518	567	578
14	380	395	498	608	672	713	750
15	380	428	534	633	706	788	829
16	493	518	539	652	713	728	871
17	498	545	561	645	846	898	944
18	518	545	602	728	880	898	944

Additionally, Slow Vital Capacity (SVC) will be evaluated as non-normalized values and Inspiratory Flow Reserve (IFR) both as a fraction and as absolute based on the following formulas:

$$\text{IFR, fraction (\%)} = (1 - (V'I, \text{max (t)} / V'I, \text{max (FVC)}) * 100$$

$$\text{IFR, absolute} = V'I, \text{max (FVC)} - V'I, \text{max (t)}.$$

The best values on the CRF, i.e. the lowest V'I, max (t) and the highest V'I, max (FVC) will be used in the calculations.

For all respiratory parameters, information of use of respiratory aid (Bi-Pap) will be given in the data listings.

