Study Endpoints	
• The Primary Endpoint is the pharmacokinetic profile of omigapil and metabolites quantified by C_{max}, C_{min}, t_{max}, $t_{1/2}$, AUC_{0-t}, AUC_{0-8h}, AUC_{0-24h}, λ_z (terminal phase rate constant) and R_o (the extent of accumulation in plasma)• The Secondary Endpoint is safety and tolerability of omigapil at the doses tested, established through the collection of Adverse Events (AEs) and Serious Adverse Events (SAEs), vital signs, oxygen saturation, standard lab parameters and electrocardiogram (ECG) assessments.• The Tertiary Endpoint is the outcome of disease-relevant clinical assessments.
• Hospital-based pulmonary function tests (PFTs) by standard spirometry.• Home-based pulmonary function tests using a child-compatible hand-held device (ASMA-1).• Hospital-based evaluation of muscle strength & function.• Motor function scales.

- Time tests (ambulatory patients only).
- Functional Scales.
- Muscle Imaging (Muscle magnetic resonance imaging (MRI) and Muscle Ultrasound)
- Collection of biomarkers

Number of Centers

1

Number of Subjects
Patient Population

Approximately 20 eligible patients will be randomly assigned to ensure a minimum of 16 patients who have completed all study procedures (3 cohorts of 4, 4, and 8-12 patients)

Inclusion Criteria

- Ambulatory and non-ambulatory patients from age 5 - 16 years (≥ 5 years old and < 17 years old) at time of screening with a clinical picture (see below) consistent with COL6-related dystrophy (COL6-RD) or LAMA2-related dystrophy (LAMA2-RD)
- Under regular review at a neuromuscular center
- On adequate double-barrier contraception (if of child-bearing potential (CBP))
- Stable on any allowed concomitant medications for 1 month prior to run in phase
- Forced Vital Capacity (FVC) 30-80% of the predicted value and confirmed at Screening and Baseline visit(s)

For patients with Collagen VI-related dystrophy (COL6-RD)– required clinical picture

- Muscle weakness: inability to walk or, if patient is still ambulatory, inability to run and > 5 s for 10 m walk

Genetics and Pathology:

- Molecular diagnosis of COL6-RD, defined by one dominant or two recessive mutation(s) in COL6A1, COL6A2 or COL6A3 known to cause the clinical picture,
OR

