13.2 Respiratory function testing (handheld ASMA-1 device)

PEF and FEV1 will be presented as non-normalized values and as percent predicted (see equations in 12.1.1). Information of use of respiratory aid (Bi-Pap) will be given in the data listings.

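### The percent-predicted PEF equation for Caucasian and Asian girls subtracts height squared, so predicted PEF and PEF%p come out negative

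*SAP*

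**What the plan says.** SAP section 13.1 makes its table of equations binding: "The equations presented in table 13.1.1 will be used for calculation of the percent predicted values". For PEF in Caucasian females under 18 years, the predicted value (the denominator) begins with a minus sign and continues "3.6181 + (0.60644 * \text{age})) - (0.016846 * (\text{age}^2) + ((0.00018623 * (\text{height}^2)) * 1". The closing brackets come only after that point, so the bracket opened before 0.016846 still encloses the height term.

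The neighbouring PEF equations differ in sign. The Caucasian male one, also after a leading minus sign, reads "0.5962 - (0.12357 * \text{age})) + (0.013135 * (\text{age}^2) + ((0.00024962 * (\text{height}^2)) * 1". The layout is the same, but a plus sign stands in front of the combined bracket. The Black or African-American female one, again after a leading minus sign, reads "1.2398 + (0.16375 * \text{age})) + ((0.00019746 * (\text{height}^2)) * 1", with height plainly added.

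Three further statements set the reach of the equation:

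- On race, "the Caucasian equation will be used also for the Asian subjects" (section 13.1).
- On height, "the height will be estimated from the ulna length for all subjects" (section 13.1).
- For the home device, "PEF and FEV1 will be presented as non-normalized values and as percent predicted (see equations in 12.1.1" (section 13.2). No table bears that number; Table 13.1.1 is the only one with such equations.

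The Protocol synopsis (Inclusion Criteria) sets the age range as "≥ 5 years old and < 17 years old) at time of screening". Neither document gives a corrected form of the female equation.

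**The concern.** A predicted peak flow must be positive and should rise with body size. As bracketed, this one falls as height rises and is negative for any realistic patient. The consequences for Caucasian and Asian girls are:

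- **Level.** PEF%p is negative, so it cannot be read as a share of normal.
- **Change.** With a negative denominator, a rise in measured PEF makes PEF%p fall. SAP section 13 calls for absolute values and changes from baseline, so improvement would be reported as decline.
- **Summaries by dose.** Means and medians would mix negative values from these girls with positive values from everyone else. The first two planned cohorts have four patients each, so one or two girls would dominate.

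The outputs concerned are Tables 14.3.1.1 and 14.3.2.1, Figures 14.3.1.2 and 14.3.2.2, and Listings 16.2.3.1 and 16.2.3.2. The listing of lung function results for patients with an adverse event of special interest (SAP section 12.1) is also affected if it carries PEF%p. The tertiary objective is to inform the design of later studies, and PEF%p in this state could not serve it.

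**Working it through.** **Inputs.** The coefficients are those of SAP Table 13.1.1. The age range is 5 to under 17 years at screening, so up to about 17.5 years after 28 weeks of participation. The documents give no patient heights, so the heights below are assumptions. The division by 60 in the PEF%p formula implies measured PEF in L/min and predicted PEF in L/s. The SAP states no predicted value, so there is no figure of its own to reproduce.

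**Formulas** (a = age in years, h = height in cm)

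- As printed: P = (-3.6181 + 0.60644a) - (0.016846a² + 0.00018623h²)
- Height added: P* = -3.6181 + 0.60644a - 0.016846a² + 0.00018623h²
- PEF%p = PEF / P / 60 × 100

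**One girl, 10 years, 135 cm**

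- Constant plus linear age term: -3.6181 + 6.0644 = 2.4463
- Age-squared term: 0.016846 × 100 = 1.6846
- Height term: 0.00018623 × 18,225 = 3.3940
- As printed: 2.4463 - (1.6846 + 3.3940) = **-2.63 L/s**
- Height added: 2.4463 - 1.6846 + 3.3940 = **4.16 L/s**
- Same age and height, Caucasian male: -0.5962 - 1.2357 + 1.3135 + 4.5493 = 4.03 L/s
- Same age and height, Black female: -1.2398 + 1.6375 + 3.5987 = 4.00 L/s

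A measured PEF of 150 L/min gives 150 / (-2.63) / 60 × 100 = -95% as printed, and 150 / 4.16 / 60 × 100 = 60% with height added. A 10% improvement to 165 L/min moves the printed value to -104.5%, an apparent fall of 9.5 points.

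**Other ages, predicted PEF in L/s**

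| Age, height | As printed | Height added | Caucasian male | Black female |
|---|---|---|---|---|
| 5 y, 105 cm | -3.06 | 1.05 | 1.87 | 1.76 |
| 8 y, 125 cm | -2.75 | 3.07 | 3.16 | 3.16 |
| 12 y, 150 cm | -2.96 | 5.42 | 5.43 | 5.17 |
| 14 y, 158 cm | -3.08 | 6.22 | 6.48 | 5.98 |
| 16 y, 162 cm | -3.12 | 6.66 | 7.34 | 6.56 |

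**Could any patient get a positive value?** The age part, -3.6181 + 0.60644a - 0.016846a², is -1.01, -0.59 and -0.20 at ages 5, 6 and 7, so no height helps there. Later, P is positive only below h = √(age part / 0.00018623). At age 10 that is √(0.7617 / 0.00018623) = 64 cm. It is 81 cm at 12, 92 cm at 14, 98 cm at 16 and 99 cm at 17-18. By the SAP's own female height formula (section 8), these heights need an ulna of about 10 cm or less. Over ages 5-18 and heights of 100-180 cm, the largest value is at 18 years and 100 cm: 1.8397 - 1.8623 = -0.02 L/s.

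**Effect on a small cohort (illustration).** Take four patients who should all read 60%, two of them girls read at -95%. The cohort mean becomes (60 + 60 - 95 - 95) / 4 = -17.5%.

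**Is the sign intended?** All the other PEF, FVC and FEV1 equations add height squared. Six of them use the same combined bracket, each with a plus sign in front, where it does no harm. The Black male FEV1 equation closes the bracket directly after age squared. The female PEF equation is the only one where a minus sign precedes the combined bracket, which points to a layout carried over without regard to the sign.

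**The case against.** The arithmetic is not in dispute. The case on the other side concerns what follows from it.

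- **The bracket may be an artefact of text extraction.** The brackets balance, but a displaced bracket would balance too. Other formulas in the same text do not balance: male height in section 8 (3 open, 2 closed) and the inspiratory flow reserve fraction in section 13.1 (4 open, 3 closed). This caution stands as far as checking the source file. The recurrence of the same layout in six other equations makes a genuine SAP error much the likelier explanation.
- **No program or output is available.** The SAP says it was written during the study, with access to the data, to document the methods used, so correct code may sit behind a mistyped formula. This stands as a condition on the rerun. It does not excuse the text: either the document misstates the method or the outputs are invalid.
- **The reach is limited.** PEF%p is one of many descriptive variables under a tertiary objective. It does not feed the primary pharmacokinetic endpoint or dose escalation, and eligibility uses FVC. Raw PEF is presented alongside it, and values near -100% would probably be noticed. All of this stands and bounds the harm.
- **The number of girls affected is unknown.** About 20 patients are planned, with no breakdown by sex or race. This also stands.

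**Conclusion.** The equation is wrong as written. For Caucasian and Asian girls in the eligible age range it gives a negative predicted PEF at any height of 100 cm or more, and at any height at all for ages 5-7. In the assumed examples the predicted value is about -2.6 to -3.1 L/s, where adding height gives 1.05 to 6.66 L/s. Levels, changes from baseline and by-dose summaries of PEF%p are then invalid for hospital spirometry and for ASMA-1.

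The conclusion rests on two assumptions: that the printed bracket matches the source file, and that girls in the trial are not shorter than about 1 m at the older ages. Whether reported results are affected depends on whether the program follows the printed text. Raw PEF, FVC%p, FEV1%p and the other three PEF equations are untouched. The point should be corrected despite the tertiary status of the endpoint, because the stated rule cannot give a usable value for a whole subgroup.

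**What to change.** 1. In SAP Table 13.1.1, close the bracket after age squared, so that the Caucasian female denominator is -3.6181 + 0.60644 × age - 0.016846 × age² + 0.00018623 × height².
2. Confirm this form against the reference cited in the table. The correction here is inferred from the other equations. It lies close to them from age 8 but below them at age 5 (1.05 against 1.76 to 1.87 L/s), so the source should be consulted.
3. Compare the analysis program with the corrected equation. If it follows the printed bracket, rerun PEF%p for Tables 14.3.1.1 and 14.3.2.1, Figures 14.3.1.2 and 14.3.2.2, Listings 16.2.3.1 and 16.2.3.2, and the special-interest adverse event listing if it shows PEF%p.
4. In section 13.2, point the cross-reference to Table 13.1.1.

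The cost is one bracket and one cross-reference in the SAP, a short code check and, if needed, a rerun of descriptive outputs. No new data are required.
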